8.4.2.1. Exposure During Pregnancy (EDP)

For both unapproved/unlicensed products and for marketed products, an EDP occurs if:

- A female becomes, or is found to be, pregnant either while receiving or having been exposed (eg, because of treatment or environmental exposure) to the investigational product; or the female becomes or is found to be pregnant after discontinuing and/or being exposed to the investigational product;
- An example of environmental exposure would be a case involving direct contact with a Pfizer product in a pregnant woman (eg, a nurse reports that she is pregnant and has been exposed to chemotherapeutic products).
- A male has been exposed (eg, because of treatment or environmental exposure) to the investigational product prior to or around the time of conception and/or is exposed during his partner's pregnancy.

If a patient or patient's partner becomes or is found to be pregnant during the patient's treatment with the investigational product, the investigator must report this information to Pfizer Safety on the CT SAE Report Form and an EDP supplemental form, regardless of

whether an SAE has occurred. In addition, the investigator must submit information regarding environmental exposure to a Pfizer product in a pregnant woman (eg, a patient reports that she is pregnant and has been exposed to a cytotoxic product by inhalation or spillage) to Pfizer Safety using the EDP supplemental form. This must be done irrespective of whether an AE has occurred and within 24 hours of awareness of the exposure. The information submitted should include the anticipated date of delivery (see below for information related to termination of pregnancy).

Follow-up is conducted to obtain general information on the pregnancy and its outcome for all EDP reports with an unknown outcome. The investigator will follow the pregnancy until completion (or until pregnancy termination) and notify Pfizer Safety of the outcome as a follow-up to the initial EDP supplemental form. In the case of a live birth, the structural integrity of the neonate can be assessed at the time of birth. In the event of a termination, the reason(s) for termination should be specified and, if clinically possible, the structural integrity of the terminated fetus should be assessed by gross visual inspection (unless pre-procedure test findings are conclusive for a congenital anomaly and the findings are reported).

If the outcome of the pregnancy meets the criteria for an SAE (ie, ectopic pregnancy, spontaneous abortion, intrauterine fetal demise, neonatal death, or congenital anomaly [in a live-born baby, a terminated fetus, an intrauterine fetal demise, or a neonatal death]), the investigator should follow the procedures for reporting SAEs.

Additional information about pregnancy outcomes that are reported to Pfizer Safety as SAEs follows:

- Spontaneous abortion includes miscarriage and missed abortion;
- Neonatal deaths that occur within 1 month of birth should be reported, without regard to causality, as SAEs. In addition, infant deaths after 1 month should be reported as SAEs when the investigator assesses the infant death as related or possibly related to exposure to the investigational product.

Additional information regarding the EDP may be requested by the sponsor. Further follow-up of birth outcomes will be handled on a case-by-case basis (eg, follow-up on preterm infants to identify developmental delays). In the case of paternal exposure, the investigator will provide the patient with the Pregnant Partner Release of Information Form to deliver to his partner. The investigator must document in the source documents that the patient was given the Pregnant Partner Release of Information Form to provide to his partner.

8.4.2.2. Exposure During Breastfeeding

Scenarios of exposure during breastfeeding must be reported, irrespective of the presence of an associated SAE, to Pfizer Safety within 24 hours of the investigator's awareness, using the CT SAE Report Form. An exposure during breastfeeding report is not created when a Pfizer drug specifically approved for use in breastfeeding women (eg, vitamins) is administered in

accord with authorized use. However, if the infant experiences an SAE associated with such a drug's administration, the SAE is reported together with the exposure during breastfeeding.

8.4.2.3. Occupational Exposure

An occupational exposure occurs when, during the performance of job duties, a person (whether a healthcare professional or otherwise) gets in unplanned direct contact with the product, which may or may not lead to the occurrence of an AE.

An occupational exposure is reported to Pfizer Safety within 24 hours of the investigator's awareness, using the CT SAE Report Form, regardless of whether there is an associated SAE. Since the information does not pertain to a patient enrolled in the study, the information is not recorded on a CRF; however, a copy of the completed CT SAE Report Form is maintained in the investigator site file.

8.4.3. Medication Errors

Other exposures to the investigational product under study may occur in clinical trial settings, such as medication errors.

Safety Event	Recorded on the CRF	Reported on the CT SAE Report Form to Pfizer Safety Within 24 Hours of Awareness
Medication errors	All (regardless of whether associated with an AE)	Only if associated with an SAE

8.4.3.1. Medication Errors

Medication errors may result from the administration or consumption of the investigational product by the wrong patient, or at the wrong time, or at the wrong dosage strength.

- Medication errors involving patient exposure to the investigational product;
- Potential medication errors or uses outside of what is foreseen in the protocol that do or do not involve the participating patient.

Such medication errors occurring to a study participant are to be captured on the medication error page of the CRF, which is a specific version of the AE page.

In the event of medication dosing error, the sponsor should be notified immediately.

Whether or not the medication error is accompanied by an AE, as determined by the investigator, the medication error is recorded on the medication error page of the CRF and, if applicable, any associated AE(s), serious and non-serious, are recorded on an AE page of the CRF.

Medication errors should be reported to Pfizer Safety within 24 hours on a CT SAE Report Form **only when associated with an SAE**.

9. DATA ANALYSIS/STATISTICAL METHODS

Detailed methodology for summary and statistical analyses of the data collected in this study is outlined here and further detailed in a statistical analysis plan (SAP), which will be maintained by the sponsor. The SAP may modify what is outlined in the protocol where appropriate; however, any major modifications of the primary endpoint definitions or their analyses will also be reflected in a protocol amendment.

9.1. Analysis Sets

1. Safety analysis set.

The safety analysis set includes all enrolled patients who receive at least one dose of study treatment.

2. Full analysis set.

The full analysis set includes all enrolled patients.

3. Per-protocol analysis set (evaluable for MTD).

The per protocol analysis set includes all enrolled patients who receive at least one dose of study treatment and who do not have major treatment deviations during the first cycle. Patients with major treatment deviations during the first cycle of treatment are not evaluable for the MTD assessment and will be replaced as needed to permit the MTD estimation. Major treatment deviations include the failure to satisfy major entry criteria (eg, confirmation of the target disease; signed informed consent) or use of other anticancer treatments during the active treatment period and disease follow-up phases other than as defined/allowed in this protocol. Major treatment deviations will also include:

- Administration of less than 75% of the planned number of doses of PF-06873600 (provided that the reduction in doses is not due to toxicity attributable to PF-06873600).
- Administration of more than 110% of the planned number of doses of PF-06873600.

4. Modified Intent-to-Treat (mITT) Population.

- The modified intent-to-treat (mITT) is the analysis population that will follow the ITT principle and include patients receiving at least 1 dose of investigational product with baseline assessment and at least 1 post baseline assessment, disease progression, or death before the first tumor assessment. The mITT population

will be used for analyses and to support conference presentations when the study is still ongoing.

5. PK analysis sets.

The PK parameter analysis population is defined as all enrolled patients treated who have sufficient information to estimate at least 1 of the PK parameters of interest. The PK concentration population is defined as all enrolled patients who are treated and have at least 1 analyte concentration.

6. Biomarker analysis set(s).

- The PD/Biomarker analysis population is defined as all enrolled patients with PD/Biomarkers evaluated at pre-and/post dose.

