Initial dose levels are provided in Table 2 and intermediate dose levels may be considered as indicated. Intra-patient dose escalation for patients enrolled in dose level 1 and 2 may be considered in consultation with the sponsor. Once the respective dose level has been declared safe, patients who have completed at least 2 Cycles of treatment at the original enrolled dose level may escalate to the next higher dose level that has cleared the DLT observation period of 28 days.

Table 2. PF-06873600 Dose Levels (Immediate Release Formulation)

DOSE LEVEL (DL)*	DOSE	TOTAL DAILY DOSE***
DL 1**	1 mg BID	2 mg
DL 2	2 mg BID	4 mg
DL 3	5 mg BID	10 mg
DL 4	10 mg BID	20 mg
DL 5 and Beyond		Escalation to continue to the MTD or desired pharmacological activity

*The proposed doses, schedule(s), and PK time points may be reconsidered or amended during the study based on the emerging safety and PK data. Intermediate doses may be considered when deemed necessary based on on-going evaluation of safety and toxicity data.

** Starting dose DL1.

*** Total daily dose may be administered in up to 3 divided doses.

In principle, all patients must be evaluated for a minimum DLT observation period of 28 days in Part 1. However, in order to be evaluable for DLT assessment patients need to have received at least 75% of planned doses unless the patient has experienced a DLT prior to receiving 75% of the planned dose.

The dose escalation in Part 1A, and 1C, dose finding in Part 1B, and each arm of the dose expansion in Part 2 of the study will stop as the applicable following criteria are met:

- The maximum sample size has been achieved (approximately 75 patients in Part 1, excluding patients enrolled in biomarker cohorts, and approximately 70 patients in Part 2);

- 6 to 12 evaluable patients (for Parts 1A, Part 1B, and Part 1C) that have been enrolled at a PF-06873600 dose level (as a single agent, in combination with letrozole, and in combination with fulvestrant, each) that is predicted to be the MTD per the mTPI method;
- All dose levels explored appear to be overly toxic, and the MTD cannot be determined.

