5.4.3.4. Dose Reductions

Following dosing interruption or cycle delay due to toxicity, the PF-06873600 dose may need to be reduced when treatment is resumed.

No specific dose adjustments are recommended for Grade 1/2 treatment -related toxicity. However, investigators should always manage their patients according to their medical judgment based on the particular clinical circumstances.

Dose reduction of PF-06873600 by 1 and, if needed, 2 dose levels, or intermediate dose levels, will be allowed depending on the type and severity of toxicity encountered. Patients requiring more than 2 dose reductions will be discontinued from the treatment and entered into the follow-up phase, unless otherwise agreed between the investigator and the sponsor.

All dose modifications/adjustments must be clearly documented in the patient's source notes and CRF.

Patients experiencing a DLT may resume dosing at the next lower dose level (if applicable) once adequate recovery is achieved at the discretion of the investigator. No dose reductions are planned for patients experiencing toxicities other than those listed as DLTs. However, patients experiencing recurrent and intolerable toxicity that does not meet the criteria for DLT (ie, recurrent transient high grade neutropenia or diarrhea) or are Grade 2 may resume dosing at the next lower dose level once recovery to Grade ≤ 1 or baseline is achieved.

Dose reductions during the DLT observation period are not permitted unless the patient experiences a DLT. However, at the discretion of the investigator or sponsor based on emerging safety data, patients may be asked to reduce their dose within the DLT window.

Recommended dose reductions for Part 1 and Part 2 are described in Table 3.

Table 3. Dose Modifications for PF-06873600-Related Toxicity

Toxicity	Grade 1	Grade 2*	Grade 3**	Grade 4
Nonhematologic	Continue at the same dose level.	Continue at the same dose level.	Withhold dose until toxicity is Grade ≤ 1 , or has returned to baseline, then resume treatment at the same dose level or reduce the dose by 1 level at the discretion of the investigator.	Withhold dose until toxicity is Grade ≤ 1 , or has returned to baseline, then reduce the dose by 1 level and resume treatment, or discontinue at the discretion of the investigator.***

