Patients not evaluable for assessment of DLT (eg, consent withdrawal in Cycle 1) will be replaced, and the safety information obtained from all patients who received at least 1 dose will be used for tolerability assessment.

When a dose level of J-LIC is deemed safe following a DLT observation period of 28 days and based on discussion by the safety review team (comprised of the Investigators and the Sponsor), Japanese participants will be able to join in Part 2 of the main study.

Japanese participants will be evaluated according to the current eligibility criteria will undergo the same study procedures and DLT evaluation period and will be evaluated using the same discontinuation criteria as participants in the dose escalation cohort of Part 1 of the main study, unless otherwise specified. The followings are only applicable in J-LIC.

1. DLT Definition:

In addition to [Section 3.1.6](#) DLT Definition, the following toxicities will be classified as DLTs if they occur in patients in the J-LIC.

- Grade 4 anemia.
- Grade 3 anemia requiring transfusions or steroids.
- Grade 3 thrombocytopenia requiring transfusions.
- Inability to complete at least 75% of the first cycle doses of PF-06873600 due to investigational product related toxicity.
- Clinically important or persistent toxicities (eg, toxicities responsible for >3 weeks dose delay) that are not included in the above criteria may also be considered a DLT following review by the investigators and the sponsor. All DLTs need to represent a clinically significant shift from baseline.

2. Eligibility criteria:

In J-LIC, the inclusion criteria #1 and #2 ([Section 4.1](#)) will be replaced with “Patients with a histological or cytological diagnosis of locally advanced or metastatic solid tumor that is resistant to standard therapy or for which no standard therapy is available.” mBC and solid tumors with known CCNE amplification will be encouraged to enroll. The specific type of

solid tumor with CCNE amplification considered after consultation between the investigator and the sponsor as necessary.

2.1. Rationale for including additional solid tumors in Japan:

The target participants for J-LIC follow the Guidelines for Clinical Evaluation Methods of Anti-Cancer Drugs in Japan.¹ Given the potential mechanism of action for the study drug, participants with mBC and other solid tumor with known to CCNE amplification will be encouraged to enroll.

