The mTPI design uses a Bayesian decision-theoretic framework and a beta/binomial hierarchical model to tailor dose-escalation and de-escalation decisions. These rules are conceptually similar to those used by the 3+3 design and all the dose-escalation decisions for a given trial can be pre-calculated under the mTPI design and presented in a two-way table.

The decision rules to "dose escalate" (E), "no change in dose" (S), "dose de-escalate" (D) or "dose de-escalate, unacceptable toxicity" (U) are described below:

Table 2 Dose Escalation Decision Rules

DLT	n=2	n=3	n=4	n=5	n=6	n=7	n=8	n=9	n=10	n=11	n=12
0	E	E	E	E	E	E	E	E	E	E	E
1	S	S	S	S	E	E	E	E	E	E	E
2	D	D	D	S	S	S	S	S	S	S	E
3		u	u	D	D	S	S	S	S	S	S
4			u	u	u	u	D	S	S	S	S
5				u	u	u	u	u	D	S	S
6					u	u	u	u	u	u	u
7						u	u	u	u	u	u
8							u	u	u	u	u
9								u	u	u	u
10									u	u	u
11										u	u
12											u

Actions to be taken: D = De-escalate the dose; E = Escalate the dose; S = Stay at the dose. U = Unacceptable toxicity.

In principle, all patients must be evaluated for a minimum DLT observation period of 28 days in both Part 1 and Part 2. However, in order to be evaluable for DLT assessment patients need to have received at least 75% of planned doses unless related to treatment emergent toxicity.

The dose escalation in Part 1A and 1C, dose finding in Part 1B, and each arm of the dose expansion in Part 2 of the study will stop as the applicable following criteria are met:

- The maximum sample size has been achieved (approximately 50 patients in Part 1, excluding patients enrolled in biomarker cohorts, and approximately 30 patients in each dose arm in Part 2);
- 6 to 12 evaluable patients (for Parts 1A, Part 1B and Part 1C) that have been enrolled at a PF-06873600 dose level (as a single agent, in combination with letrozole, and in combination with fulvestrant, each) that is predicted to be the MTD per the mTPI method;
- All dose levels explored appear to be overly toxic, and the MTD cannot be determined.

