6.3. Per-protocol analysis set (evaluable for MTD)

The per protocol analysis set includes all enrolled patients who receive at least one dose of study treatment and who do not have major treatment deviations during the first cycle. Patients with major treatment deviations during the first cycle of treatment are not evaluable for the MTD assessment and will be replaced as needed to permit the MTD estimation. Major treatment deviations include the failure to satisfy major entry criteria (eg, confirmation of the target disease, signed informed consent) or use of other anticancer treatments during the active treatment period and disease follow-up phases other than as defined/allowed in this protocol. Major treatment deviations will also include:

- *Administration of less than 75% of the planned number of doses of PF-06873600 during DLT observation period (provided that the reduction in doses is not due to toxicity attributable to PF-06873600).*
- *Administration of more than 110% of the planned number of doses of PF-06873600 during DLT observation period.*

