9.2. Statistical Analyses

9.2.1. Primary Analysis

Dose Limiting Toxicity (DLT) is the primary endpoint of the study, which will be summarized by dose level using the Per Protocol Analysis Set for patients in the dose escalation portion of the study. A listing of the DLTs will also be provided.

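### DLT evaluability is defined differently in the escalation text and in the per-protocol set, so a patient cut short by non-DLT drug toxicity enters the reported DLT rate as a non-DLT

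*Protocol*

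**What the plan says.** Four places in the current text state who is evaluable for DLT or MTD assessment.

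- Protocol 3.1.5 requires "at least 75% of planned doses unless the patient has experienced a DLT prior to receiving 75% of the planned dose". A DLT is the only exemption.
- Protocol 9.1, under the per-protocol set, makes a shortfall below 75% of the number of doses a major treatment deviation, but only "provided that the reduction in doses is not due to toxicity attributable to PF-06873600".
- SAP 6.3 repeats that rule and ties it to Cycle 1: "less than 75% of the planned number of doses of PF-06873600 during DLT observation period", with the same drug-toxicity exemption.
- SAP 2.1.4 says that "patients need to have received at least 75% of planned doses unless related to treatment emergent toxicity". It has no attribution test.

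SAP 9.2.1 names the population for the Part 1 primary endpoint: DLTs are "summarized by dose level using the Per Protocol Analysis Set".

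One cohort is treated differently. For the Japan lead-in cohort (J-LIC), Protocol Appendix 7.1 adds to the DLT definition "Inability to complete at least 75% of the first cycle doses of PF-06873600 due to investigational product related toxicity". It introduces that list with the limit "The followings are only applicable in J-LIC".

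On dose changes in Cycle 1, Protocol 5.4.3.4 states "Dose reductions during the DLT observation period are not permitted unless the patient experiences a DLT". The next sentence lets the investigator or sponsor ask for a reduction in that window at their discretion.

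**The concern.** Evaluability for DLT should have one answer per patient, because it fixes the denominator of the Part 1 primary summary. Here the rule written for escalation and the rule written for reporting part company over one kind of patient: someone who loses more than a quarter of Cycle 1 dosing to drug toxicity that does not meet the DLT definition. Protocol 3.1.5 calls that patient non-evaluable. The per-protocol set keeps the patient and, since no DLT occurred, counts a non-DLT.

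That patient was under-exposed because the drug was not tolerated. Scoring the patient as evidence of tolerability can only lower the reported rate or leave it unchanged. A reader of the study report could not tell from the documents whether the denominators shown are those on which escalation was decided.

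**Working it through.** **The plan's own figure.** Protocol 9.2.2 tabulates the probability of escalating, assuming escalation after 0/3 or 1/6 DLTs. With true DLT rate p, P = (1−p)³ + 3p(1−p)²(1−p)³. For p = 10% to 90% this gives 0.906, 0.709, 0.494, 0.309, 0.172, 0.082, 0.032, 0.0088 and 0.001, which matches all nine printed values. The formula takes every patient as evaluable, so it does not settle which rule applies.

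**The rules side by side.** Twice-daily dosing for 28 days is 2 × 28 = 56 doses; 75% of 56 is 42. None of the patients below has a DLT.

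| Cycle 1 course | Doses taken | 3.1.5 | 9.1 and SAP 6.3 | SAP 2.1.4 |
|---|---|---|---|---|
| Held Days 8–14 for drug toxicity, then resumed | 42/56 = 75.0% | in | in | in |
| Same, one further dose missed for that toxicity | 41/56 = 73.2% | out | in | in |
| Stopped after Day 7, drug toxicity | 14/56 = 25.0% | out | in | in |
| Stopped after Day 7, toxicity attributed only to the endocrine partner (Part 1B) | 14/56 = 25.0% | out | out | in |

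Rows 2 and 3 are the conflict between the escalation rule and the reporting set. Row 4 shows that the two SAP sections also differ from each other.

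**Whether such a patient is realistic.** Under Protocol 3.1.6, Grade 3 neutropenia without fever or infection is not a DLT, and Grade 4 neutropenia is one only if it lasts more than 7 days. Table 3 in 5.4.3.4 nevertheless withholds drug for Grade 3 hematologic toxicity until Grade 2 or better, and 5.4.3.3 allows delays of up to 4 weeks. A hold one dose longer than 7 days is enough to fall below 75%.

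**Effect on the reported rate.** Let the SAP 6.3 set at a dose level have n patients and x DLTs, with m of the n being non-DLT drug-toxicity shortfalls.

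- SAP 6.3 rule: x/n.
- 3.1.5 rule: x/(n − m).
- Shortfalls counted as DLTs, as in the J-LIC: (x + m)/n.

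Protocol 3.1.7 puts 6 to 12 patients at each MTD/RDE. Taking x = 1 and m = 1 as an illustration:

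- n = 6: 1/6 = 16.7%, 1/5 = 20.0%, 2/6 = 33.3%.
- n = 12: 1/12 = 8.3%, 1/11 = 9.1%, 2/12 = 16.7%.

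With x = 0, which Appendix 7.1 reports for 25 mg immediate release, the first two rules both give 0% and only the third moves, to m/n. The value of m is not in the documents.

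**The case against.** The strongest reply is that the reported summary has one named population. SAP 9.2.1 assigns it to the per-protocol set, and Protocol 9.1 and SAP 6.3 define that set with the same threshold and exemption. Protocol 3.1.5 and SAP 2.1.4 are study-design text. This is right as far as it goes. A reader might infer that the population of the DLT table is undefined, and it is not. What stands is that this population keeps patients whom the escalation rule discards, and scores them as non-DLTs.

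Three other readings go too far.

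- **That escalation went wrong.** Table 1 gives stay at 1/5 and escalate at 1/6, so the rule is not neutral. But those decisions are closed. They were also not purely mechanical: Protocol 3.1.1 to 3.1.3 bring in safety-team review and all available safety, PK and PD data. The documents show no decision that turned on this.
- **That the 75% must be measured in milligrams.** Protocol 9.1 and SAP 6.3 count doses. A patient on a reduced dose who takes all 56 has no dose-count deviation and is in the set. One may prefer an amount-based threshold, but a rule exists.
- **That a new listing is needed.** SAP 9.2.4 already lists planned and administered dose, percentage of planned dose, reductions and interruptions by patient and cycle, with reasons for dosing changes.

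It is also fair to say that the 3.1.5 rule removes patients because they had toxicity, which is informative exclusion. That is why alignment alone is not enough and a bounding summary should go with it. The choice of 3.1.5 as the common rule has support: the amendment history shows that its exemption was changed in August 2020 from treatment-emergent toxicity to a DLT. SAP 2.1.4 still has the replaced form, although SAP version 4.0 says that it is updated through Amendment 9.

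**Conclusion.** The rule is wrong as written, because the sections are inconsistent; severity is minor. Outside the J-LIC, a patient below 75% because of non-DLT drug toxicity is non-evaluable for escalation under Protocol 3.1.5 but is counted as a non-DLT in the primary DLT summary. Where that dose level also has at least one DLT, the reported rate is lower than under the 3.1.5 rule. In the six-patient illustration the difference is 3.3 percentage points (16.7% against 20.0%), with 33.3% as the upper bound.

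This rests on assumed values of x and m. The frequency of such patients is unknown. Protocol Appendix 8 records that the sponsor decided to terminate the study in September 2022, so the live consequence is the reported DLT summary and not any future dosing decision.

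**What to change.** Align Protocol 9.1, SAP 6.3 and SAP 2.1.4 with 3.1.5, so that a DLT is the only exemption from the 75% requirement. Add one sensitivity DLT summary by dose level that counts drug-toxicity-driven shortfalls below 75% as DLTs, using the J-LIC criterion and keeping these patients in the denominator. Label it an upper bound, since some of them would not have had a DLT.

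If the protocol is not amended again, keep the SAP 6.3 set as primary. Add a summary under the 3.1.5 rule and the upper-bound summary, and state in the study report which rule governed escalation. SAP section 2 already provides for describing departures from the plan there.

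In either case, flag Cycle 1 reductions made without a DLT in the existing SAP 9.2.4 listings. The 75% threshold does not need redefining in milligrams.

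The cost is a slightly smaller evaluable set and one or two extra tables. No new data are needed: Protocol 5.4.3.4 requires dose changes to be recorded in the CRF, and SAP 9.2.4 already uses planned and administered dose.
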